11.8.5 Time Tolerance Windows and Total Blood Volume

The time tolerance window for blood samples collected during the confinement period will be within the hour pre-dose for the pre-infusion sample, ± 3 minute for all samples collected before 8 hours post-start of infusion and ± 15 minutes for all subsequent samples collected up to 48 hours post-start of infusion. The time tolerance window for return visit samples will be ± 1 day on Days 5, 8 and 15, ± 2 days for Days 22 and 29, and ± 3 days for Day 60. The time tolerance window for CSF samples on Day 2 is ± 3 hours. Sample collections done outside the pre-defined time windows will not be considered as protocol deviations since actual post-start of infusion sampling times will be used for PK and statistical analyses. Unless otherwise specified or for subject safety, when blood draws and other procedures coincide, blood draws will have precedence. When timepoints for ECGs, vital signs, and blood draws coincide, procedures will be carried out in the said order. A dead-volume intravenous catheter will be used for blood collection to avoid multiple skin punctures, when appropriate. Otherwise, blood samples will be collected by direct venipuncture.

The planned volume of blood to be collected during the study, including that collected for eligibility and safety purposes, should not exceed 250 mL. Additional tests or blood draws could be performed, if deemed required by the Investigator or study staff.

Serum and CSF samples will be collected and processed as per the Analytical Methodology Information Sheet / Laboratory Manual.

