3.6 Subject Withdrawal and Replacement

Subjects who withdraw, or are withdrawn, from the study for safety and tolerability reasons after

This document is confidential.

dosing will not be replaced. However, subjects who withdraw or are withdrawn from the study after dosing for reasons other than safety and tolerability, may be replaced. The total number of subjects dosed (including potential replacement subjects) will remain within a maximum of 10 subjects per cohort.

This document is confidential.

4. Endpoints

- Primary endpoints:
 - Incidence, nature, relatedness, and severity of AEs.
 - Changes in vital signs measurements, physical examination, clinical laboratory test findings, and 12-lead electrocardiogram (ECG) results.
- Secondary endpoints:
 - Serum PK parameters for NS101 will include the following:
 - area under the concentration-time curve, from time zero to 24-hours (AUC_{0-24})
 - area under the concentration-time curve from time zero until the last observed concentration (AUC_{0-t})
 - area under the concentration-time curve from time zero to infinity ($AUC_{0-\infty}$)
 - maximum observed concentration (C_{max})
 - time when the maximum concentration is observed (T_{max})
 - terminal elimination half-life ($T_{1/2 el}$)
 - elimination rate constant (K_{el})
 - apparent body clearance (Cl)
 - apparent volume of distribution (V_z)
 - Concentrations of NS101 in CSF for Cohorts 5 to 8
 - Serum to CSF ratio of NS101 concentrations
 - Immunogenicity of NS101, measured as the number and percentage of subjects who develop detectable anti-drug antibody (ADA) and neutralizing antibody (NAb)
- Exploratory endpoints:
 - Effect (E): variation of level of FAM19A5 ($\Delta FAM19A5$) following administration of NS101:
 - PD: Change in baseline of FAM19A5 levels
 - The following PD parameters in plasma:
 - $AUEC_{0-t}$
 - maximal observed effect (E_{max})
 - time of maximal observed effect (TE_{max})
 - Concentrations of FAM19A5 in CSF

This document is confidential.

5. Analysis Populations

All subjects' inclusion status into each analysis population will be determined after database lock.

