Only data from protocol scheduled (“nominal”) visits / timepoints will be included in the summary tables. Data from unscheduled visits will not be included in the summary tables (unless they were used as baseline) but will be included in the listings.

In the case of a repeat test, both assessments will be presented in the listings. If a repeat measurement was performed due to the first measurement being outside the normal range for the given assessment and the second assessment confirms the first measurement, then only the first measurement will be used for analysis and the second assessment will be considered an unscheduled timepoint. In the same case, if the second assessment falls within normal ranges, then the second assessment will be used for analysis of that timepoint. In all other cases, the first measurement will be taken as the assessment to be used for the analysis.

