11.3 Clinical Laboratory Evaluations

The following clinical laboratory evaluations will be performed: biochemistry, hematology, coagulation, serology, and urinalysis.

Clinical laboratory values will be flagged as either high or low based on the reference ranges provided by the laboratories for each laboratory parameter.

Actual values and changes from baseline for quantitative clinical laboratory test results will be summarized by cohort/treatment for each time point using descriptive statistics (n, mean, SD, min, median, and max). Unscheduled visits will not be included in the summary tables (unless they were used as baseline).

Shift tables from baseline to each scheduled post-baseline visit, will be generated for categorical clinical laboratory test results using normal; abnormal (NCS, CS), or missing categories as appropriate by cohort/treatment for each time point for the safety set.

Individual clinical laboratory results and reference ranges will be presented in data listings. Unscheduled visits will be included in data listings.

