11.4 Vital Signs

Actual values and change from baseline will be summarized by cohort/treatment at each time point using descriptive statistics. Classifications of findings will be shown in a shift table with changes from baseline to post baseline, in addition to being included in the listings. The classifications of findings include “normal”, “abnormal, not clinically significant”, or “abnormal, clinically significant”. Orthostatic vital signs were collected for Cohort 1 to 4. Orthostatic vital signs collection stopped due to Protocol Amendment II and only screening visit data for subject 4001 to 4005 are applicable for cohort 4. These data will be listed separately.

11.5 12-Lead ECG

Actual values and change from baseline for the ECG parameters will be summarized by cohort/treatment at each timepoint using descriptive statistics.

Findings of 12-lead ECGs will be classified as either “normal”, “abnormal, not clinically significant”, or “abnormal, clinically significant”. A shift table for categorical variables will also be created.

All safety ECG data will be listed.

This document is confidential.

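### Unscheduled post-dose laboratory, vital-sign and ECG values are kept out of the summary and shift tables, and no any-time or worst-value table makes up for it

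*SAP*

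**What the plan says.** The second primary endpoint in SAP 4 is "Changes in vital signs measurements, physical examination, clinical laboratory test findings, and 12-lead electrocardiogram (ECG) results". The first is the incidence, nature, relatedness and severity of adverse events.

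The general rule in SAP 6.2 is "Data from unscheduled visits will not be included in the summary tables (unless they were used as baseline"; the same sentence sends these data to the listings. SAP 11.3 restates it for laboratory data, "Unscheduled visits will not be included in the summary tables (unless they were used as baseline", and adds "Shift tables from baseline to each scheduled post-baseline visit, will be generated for categorical clinical laboratory test results". For vital signs, SAP 11.4 says "Classifications of findings will be shown in a shift table with changes from baseline to post baseline", without limiting that table to scheduled visits, but the general rule in 6.2 still governs it. SAP 11.5 summarises ECG parameters by timepoint and adds a shift table. None of these sections describes a worst-post-baseline or any-time summary.

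SAP 6.3 takes baseline as the last non-missing value before the infusion, unscheduled values included, and counts as post-baseline only measurements made after the infusion ends.

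The protocol expects measurements outside the schedule. Section 11.8.5 says "Additional tests or blood draws could be performed, if deemed required by the Investigator or study staff", and section 11.9 allows safety measurements to be repeated under site procedures or on the investigator's request.

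**The concern.** An unscheduled safety measurement is usually made because someone suspects a problem. Leaving such values out of by-visit means is ordinary practice, since they have no nominal timepoint. The difficulty is that by-visit tables are the only tables planned for these three domains. As planned, they describe subjects at fixed times and leave out readings prompted by symptoms or by an earlier abnormal result.

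At stake is how completely the report's tables describe the second primary endpoint. This is a first-in-human study with six active subjects per dose, in which Protocol 5.4.1 anticipates infusion reactions and some cytokine release. A short excursion caught only by an extra reading, and not recorded as an adverse event, would be visible only to someone reading the listings line by line.

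**Working it through.** The SAP gives no figure on this point to reproduce. The check sets the rules beside the schedule.

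**1. Laboratory tests.** Protocol 11.9.6 schedules post-dose samples on Days 3, 8, 15 and 29, and at study exit on Day 60. The nominal gaps are 8 − 3 = 5, 15 − 8 = 7, 29 − 15 = 14 and 60 − 29 = 31 days. An extra sample within any gap, or before Day 3, is unscheduled. Under SAP 6.2 and 11.3 it enters neither the descriptive tables nor the shift tables.

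**2. Vital signs and ECG.** Protocol 11.9.1 and 11.9.2 schedule both before the infusion and then first at 1.5 h after its start. Protocol 11.6 gives an infusion of about 60 minutes.

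| Time of reading, from start of infusion | Scheduled? | Post-baseline under SAP 6.3? | In summary or shift tables? |
|---|---|---|---|
| 0 to about 1 h (infusion running) | No | No | No, on both counts |
| About 1 h to before 1.5 h | No | Yes | No: unscheduled |
| 1.5 h and later scheduled times | Yes | Yes | Yes |
| Between later scheduled times | No | Yes | No: unscheduled |

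Protocol 11.10 allows an infusion slowed after a reaction to run for up to 3 h (± 10 minutes). The scheduled 1.5 h and 2 h vital signs and the 1.5 h ECG could then precede the end of infusion. Read literally, SAP 6.3 would not count them as post-baseline although SAP 6.2 tabulates them as scheduled.

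**3. ECG persistence.** Protocol 9.2.1 includes QTcF criteria that must persist for at least 10 or 30 minutes. Scheduled Day 1 ECGs after the infusion are at 1.5, 4, 8 and 12 h, hours apart, so documenting persistence needs extra recordings. Those recordings are unscheduled.

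**4. The other route into a primary-endpoint table.** SAP 11.2 defines a treatment-emergent event by onset at or after dosing, not by type of visit, and an adverse event may be an abnormal laboratory finding. A finding recorded as an event is therefore counted by system organ class, preferred term, severity and relationship. The measured value is not carried over. SAP 11.6 gives an explicit rule that a clinically significant change becomes an adverse event, but only for physical examination. For laboratory, vital-sign and ECG values the step depends on the general definition and on judgement. An unscheduled value classed as abnormal but not clinically significant would normally stay in the listings.

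**5. Scale.** SAP 3.3 gives 6 active and 2 placebo subjects in each of 8 cohorts. One subject is 1/6 = 16.7% of an active dose group, or 1/(2 × 8) = 1/16 = 6.3% of the pooled placebo group.

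**6. Precedent in the same SAP.** The table in SAP 10 of subjects with at least one positive antibody result expressly counts unscheduled visits.

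**The case against.** The strongest reply is that nothing is hidden. SAP 6.1 and 6.2 list all data, cohorts are small enough for listings to be read, no inferential safety analysis is planned, and clinically important findings should appear as adverse events. Dose escalation rests on the Safety Review Committee and on stopping rules applied to individual events, not on these final tables. All of this stands and limits the consequence to reporting.

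Four stronger readings are tempting, and the documents do not support them.

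- A reader might infer that symptom-triggered findings cannot reach any primary-endpoint table. They can, through the adverse-event tables.
- A reader might infer that the exclusion is total. Under SAP 6.2 a within-range repeat replaces an out-of-range first value; SAP 6.3 lets a nominal value average readings around a timepoint; and SAP 6.4 says that for withdrawals other than withdrawal of consent all captured data enter the safety summaries, which does not fit easily with 6.2. Scheduled values classed as not clinically significant do appear in the shift tables, and injection-site scores at 0.5 and 1 h are scheduled and tabulated.
- A reader might see unfair asymmetry in allowing an unscheduled value as baseline. Taking the last pre-dose value is an ordinary definition and admits normal and abnormal values alike.
- A reader might use the gaps between laboratory draws to estimate what is lost. The gaps describe the protocol's schedule. The SAP rule loses a value only if an unscheduled sample is taken, and the documents give no frequency for that.

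A worst-value table also has a bias of its own: subjects measured more often have more chances of an extreme. That objection stands and has to be disclosed alongside the table.

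**Conclusion.** The point holds as a reporting gap in the second primary endpoint. Unscheduled post-dose laboratory, vital-sign and ECG values reach a primary-endpoint table only when recorded as adverse events, without the measurement; otherwise they are only listed. Vital signs and ECGs taken during the infusion are outside the change-from-baseline tables both because they are unscheduled and because of the definition in SAP 6.3.

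The number of values affected is unknown. The 16.7% figure shows what one subject weighs in a dose group; it is not an estimate of the loss. The conclusion rests on the SAP text: the table shells are a separate document, and it is assumed that they add no any-time table that the SAP does not describe. Review during the study is not affected. The change is worth making because it is cheap and concerns a primary endpoint.

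**What to change.** 1. Keep the by-timepoint tables on scheduled data. State in SAP 6.2 that the exclusion of unscheduled visits applies to by-timepoint summaries only, and reconcile this with SAP 6.4.
2. Add to SAP 11.3, 11.4 and 11.5 one any-time table per domain: shift from baseline to the worst post-dose category (normal; abnormal, not clinically significant; abnormal, clinically significant; with high and low for laboratory tests), plus the maximum and minimum change from baseline for quantitative measures. Use all scheduled, unscheduled and repeat values, by actual treatment, in the safety population.
3. For these tables, define post-baseline in SAP 6.3 as after the start of infusion. Without this, readings during the infusion would still be left out.
4. Report the number of measurements per subject with each table, so that the effect of more frequent measurement on extremes can be seen. This discloses the bias; it does not remove it.

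The cost is SAP wording and three further tables from data already collected. No study procedure changes.

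### Under SAP 6.2 an out-of-range safety reading whose repeat is in range is replaced in the tables, and no planned table counts the replaced readings

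*SAP*

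**What the plan says.** SAP 6.2 (Summary Statistics) fixes the analysis value when a scheduled assessment is repeated. If the repeat was prompted by an out-of-range first reading and confirms it, the first reading is used. If the repeat is in range: "In the same case, if the second assessment falls within normal ranges, then the second assessment will be used for analysis of that timepoint". Otherwise, "In all other cases, the first measurement will be taken as the assessment to be used for the analysis". The raw record is kept: "In the case of a repeat test, both assessments will be presented in the listings". Summary tables are confined to scheduled timepoints, and unscheduled values enter only when they served as baseline.

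The planned safety displays are:

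- **Laboratory (SAP 11.3):** descriptive statistics of values and changes by timepoint. "Clinical laboratory values will be flagged as either high or low based on the reference ranges provided by the laboratories". "Shift tables from baseline to each scheduled post-baseline visit, will be generated for categorical clinical laboratory test results".
- **Vital signs (SAP 11.4):** descriptive statistics by timepoint. "Classifications of findings will be shown in a shift table with changes from baseline to post baseline".
- **ECG (SAP 11.5):** descriptive statistics by timepoint. "A shift table for categorical variables will also be created".

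Protocol 11.9 leaves repeats to site SOPs or investigator request and states no interval. SAP 6.3 takes baseline as the last non-missing pre-infusion value, repeats included. It also allows a nominal timepoint value to be an average of several values around the timepoint.

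**The concern.** Changes in vital signs, laboratory findings and ECG are a primary endpoint (SAP 4). They are assessed descriptively only, with 6 active subjects per dose level, so one or two transient abnormalities can be the whole signal in a dose column.

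A repeat can come back in range for two reasons: the first reading was noise, or it was real and the effect has passed. SAP 6.2 treats these alike. Without a stated interval, nothing in the documents ensures that the repeat tests error rather than recovery. If replaced readings are counted nowhere, a short-lived effect at some doses could be found only by reading subject listings, without a comparison by dose against placebo.

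**Working it through.** **1. Tracing the rule through the tables.** The plan states no figure on this point, so there is none to reproduce. The by-timepoint statistics and shift tables in SAP 11.3 to 11.5 take the selected value. None is defined on the worst post-dose value, on any excursion, or on replaced readings. High and low laboratory flags are assigned, but no table is stated to count them, and the laboratory shift table is described for categorical results. For quantitative laboratory tests the affected summaries are therefore mean, SD, median, minimum and maximum. The adverse-event tables in SAP 11.2 pick up an excursion only if it is reported as an event. The table shells are in a separate document that was not available; SAP 1 says they cover the displays referred to in the SAP.

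**2. Direction.** Replacement runs only from out-of-range to in-range. Relative to the scheduled readings, tabulated abnormality can fall but cannot rise.

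**3. Illustration (all inputs assumed).** A reading is the subject's value plus independent error, with total SD 1, limits ±1.96 SD and test-retest correlation r = 0.5, 0.7 or 0.9. A drug excursion of 2 SD is present at the scheduled reading. A share q of out-of-range readings is repeated.

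First reading abnormal: P1 = 1 − Φ(1.96 − 2) + Φ(−1.96 − 2) = 51.6%, or 3.1 of 6.

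Tabulated abnormal = (1 − q) × P1 + q × P(both readings out of range). If the excursion has gone by the repeat, simulation puts the last term at about 2.5% for every r. Hence:

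- q = 20%: 0.8 × 51.6 + 0.2 × 2.5 = 41.8% (2.5 of 6)
- q = 50%: 0.5 × 51.6 + 0.5 × 2.5 = 27% (1.6 of 6)
- q = 100%: 2.5% (0.2 of 6)

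If all are repeated but half the excursion remains, 13.7–16.8% is tabulated; if it is fully sustained, 35.0–44.4%.

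With the excursion at one of the 5 post-dose laboratory timepoints (Days 3, 8, 15, 29, 60), gone by the repeat and all repeated, 56–59% of subjects have an abnormal first reading at some timepoint, against 5–6% after replacement. The tabulated mean shift at the affected timepoint falls from 2.0 SD to 0.8–1.0 SD.

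**4. No drug effect.** If all are repeated, 5.0% abnormal falls to 0.9–3.0%, and 72–97% of the removed values belong to subjects truly in range. Shifts under the present 6.2 and 6.3 rules are balanced: normal-to-abnormal against abnormal-to-normal is 0.78/0.77%, 1.09/1.09% and 1.07/1.10% for the three values of r. Changing 6.2 alone would give 2.7–4.7% against 0.6–0.8%.

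**5. Background of a table counting all first readings, no effect.** At one timepoint it is 5% (0.3 of 6). At any time, per parameter:

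| Assessment | Post-dose timepoints | Any first reading out | Per 6 active | Any confirmed |
|---|---|---|---|---|
| Laboratory | 5 | 10–18% | 0.6–1.1 | 3.6–5.5% |
| ECG | 12 | 13–32% | 0.8–1.9 | 6.5–7.5% |
| Vital signs | 14 | 14–35% | 0.8–2.1 | 7.2–8.0% |

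Pooled placebo is 8 × 2 = 16 subjects, so the laboratory background there is 1.6–2.9. Between 11% and 43% of the subjects flagged were already out of range at a single baseline reading.

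**The case against.** Confirming an abnormal value before acting on it is ordinary practice. The rule is pre-specified and applies to active and placebo alike. When there is no effect it mostly removes noise, and with the 6.3 baseline it leaves shifts balanced. Both readings stay in the listings. All of this stands, and it is why the rule itself need not change.

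It is also fair that the only cardiovascular effect the protocol reports, the monkey heart-rate decrease in section 5.2.2, lasted up to 22 hours; an effect like that could show at several scheduled readings. The gap concerns short-lived effects.

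The illustration has limits. Its inputs are assumed. The vital-sign and ECG shift tables use normal and abnormal classes (clinically significant or not) rather than ±1.96 SD limits. For quantitative laboratory tests the SAP is not stated to produce an abnormality count at all, so the percentages there show what first readings would reveal, not a planned table.

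A reader might infer that every short-lived excursion will be tabulated as normal. The documents do not support that: the excursion must have been repeated because it was out of range, and the repeat must be in range. A reader might also infer that dose-escalation decisions are affected. Nothing says that Safety Review Committee review uses the 6.2 selection, and adverse-event reporting is unchanged.

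**Conclusion.** The concern holds in a conditional form. A post-dose excursion that is repeated for being out of range and has resolved by the repeat drops out of every table described in SAP 11.3 to 11.5, unless it is separately reported as an adverse event. This is a gap in final reporting on a primary endpoint. It is neither a contradiction in the plan nor a loss of data.

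Its size in this trial cannot be stated. In the illustration it ranges from modest (3.1 against 2.5 of 6 subjects if 20% are repeated) to nearly complete (3.1 against 0.2 of 6 if all are repeated and the excursion has gone). These figures rest on a 2-SD excursion, ±1.96 SD limits and r between 0.5 and 0.9.

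Two side points need only a sentence each in the SAP. The averaging option in 6.3 competes with the 6.2 rule. Also, 6.3 counts only readings after the end of infusion as post-baseline, while Protocol 11.10 allows a slowed infusion to run up to 3 hours. The scheduled 1.5 h and 2 h values are not stated to be dropped, so this second point is a clarification only.

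**What to change.** Keep the 6.2 and 6.3 selection rules. Add to SAP 11.3 to 11.5 one table, by treatment and parameter with pooled placebo, of subjects with a post-dose out-of-range or abnormal laboratory, vital-sign or ECG reading, including first readings replaced under 6.2. The table should:

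- show counts by scheduled timepoint and at any time;
- mark each reading as confirmed, not confirmed or not repeated;
- split subjects by baseline status (in range, or already out of range), so that treatment-emergent values can be seen;
- count every reading after the start of infusion as post-dose.

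State in 6.3 that the 6.2 rule, not the average of a set of values, sets the timepoint value when a reading is repeated. Do not alter 6.2 alone, since that would unbalance the shifts against the 6.3 baseline.

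The cost is one extra table from data already collected, with no change to the planned tables. Its drawback is the noise background (about 5% per timepoint, 10–35% per parameter at any time), which is why the confirmation marks, baseline split, timepoint rows and placebo column are needed.
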